To calculate the sample size, we used data from the publication by Ramos Peñafiel⁶³, where a decrease in the expression pattern of ABCB1 gene expression from high to low expression after metformin administration was 50%.

The sample size calculation was based on the formula for estimating a proportion, with a confidence level of 95% and a precision of 5%:

$$n = \frac{Z_{\alpha}^2 * p * q}{d^2}$$

A sample number of 8 patients in each group is obtained, assuming a loss of 20%, 10 patients are calculated for each group.

Definition of the variables to be evaluated and how they are to be measured

Variable	Conceptual Definition	Unit of measurement	Type of variable	Coding
Age	Time elapsed in years since birth.	Years	Quantitative	Not applicable

Gender	Male or female phenotype of the person.	Male/female	Qualitative Dichotomous	0: male 1: female
Leukocyte count at diagnosis	Number of total leukocytes reported on complete blood count at diagnosis.	X10/ml ³	Quantitative	Not applicable
Hemoglobin at diagnosis	Measurement of the amount of oxygen transport protein reported in initial complete blood count.	g/dL	Quantitative	Not applicable
Platelet count at diagnosis	Measurement of the number of platelet fragments produced by the megakaryocytes, reported in the initial complete blood count.	X10/ml ³	Quantitative	Not applicable
Immunophenotype of leukemia lymphoblastic	Cellular variant of acute lymphoblastic leukemia	B/ T	Qualitative dichotomous	0: strain B 1: lineage T
Cytogenetic alterations	Alterations in the genetic structure of leukemic cells.	None/ t(9;22)/ t(12,21)/ t(4,11), other	Qualitative polytomous	0: none 1: t(9;22), 2: t(12,21) , 3: t(4,11), 4: other
MDR-1 and AMPK gene expression.	Amplification of gene expression by RT-PCR	No expression / low expression / high expression expression	Qualitative polytomous	0: not expressed 1: high expression 2 low expression
Pre-phase response with prednisone	Decrease in total peripheral blood blast count less than 1000 after 7 days of steroid (day 0)	Present/absent	Qualitative dichotomous	0: Yes 1: No
Morphological status at day +14	Presence of blasts in bone marrow sample per day +14 referral induction	M1, M2, M3	Qualitative polytomous	0: M1 1: M2 2: M3
Morphological response at the end of induction	Presence of blasts in the bone marrow aspirate at the completion of remission induction phase.	M1, M2, M3	Qualitative polytomous	0: M1 1: M2 2: M3

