Minimal residual disease at the end of induction.	Flow cytometry measurement of the presence of 1x10 ⁻³ blasts.	Positive /Negative	Qualitative dichotomous	0: positive 1: negative
Relapse	Presence of blasts in bone marrow after remission has been achieved.	Present/absent	Qualitative dichotomous	0: absent 1: present

Time to relapse	Time from diagnosis of leukemia to relapse	Days	Quantitative	Not applicable
Death	Cessation of life	Present/absent	Qualitative dichotomous	0: absent 1: present
Time to death	Time from leukemia diagnosis to death	Days	Quantitative	Not applicable

Table 1. Variable definitions.

PROCEDURES

Patients with a newly morphological diagnosis of ALL at the Hospital General de México "[name]" will be invited to participate in this trial, and informed consent will be requested from parents and participants.

The data collection is obtained from the patients chart such as age, gender, leukocyte count, hemoglobin, platelet count and immunophenotype.

Peripheral blood samples will be collected in EDTA tube. The sample will be centrifuged obtaining mononuclear cells, and the analysis of ABCB1 and AMPK expression will be performed. This will be done on samples obtained before the start of treatment and at the end of the induction phase. Samples will be collected by peripheral vein puncture, and mononuclear cells will be separated using density gradient. Mononuclear cells are separated and suspended in PBS medium and stored at -70°C . RNA isolation is performed using TRIzol® (Invitrogen/life Technologies), and will be stored at -80°C until use. For cDNA synthesis, 2g of RNA, final volume of 20L will be combined with 200U of MMLV RT enzyme (Invitrogen, Carlsbad, CA, USA).

Expression of mRNA levels will be measured using the TaqMan gene expression assay (Applied Biosystems Foster city, CA, USA). The cut-off point between low and high expression will be determined according to mean values obtained in healthy controls, selected during case recruitment in a 2:1 ratio for each case.

Regarding treatment, patients will be randomized into 2 groups, where in both cases the conventional remission induction treatment will be given, and to intervention group metformin will be added at a dose of 1000mgm2Seday, divided into two doses, with a maximum dose of 850mg every 8 hour, orally.

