The assignment will be made by means of the block randomization technique, in which, from a table of random digits, two-digit numbers are selected, each of which corresponds to a block of 6 patients, to which the intervention is assigned in the corresponding sequence.

All patients will start treatment with steroid window, with prednisone at a dose of 60mgm2Seday (maximum dose 100mg/d), for 7 days (from day -7 to-1). Patients in the study group (treatment with conventional chemotherapy + metformin) are added metformin hydrochloride orally, at a dose of 1000mgm2Seday, divided into two doses, with a maximum dose of 850mg every 8 h starting from day -7 of treatment. On day 0 the response to the pre-phase with prednisone (60mgm2scd) will be assessed by means of blood biometry with differential count and blast count.

Both groups will start remission induction and consolidation treatment according to the Institutional High Risk protocol, which includes administration of vincristine, prednisone, daunorubicin and L-asparaginase. Patients assigned to intervention group will also continue with metformin at the established doses.

A bone marrow exam will be performed at day +14 of remission induction to determine the marrow response to chemotherapy. A bone marrow aspirate will be performed at the end of remission induction to evaluate the response to this phase of treatment with morphological study and minimal residual disease, as well as determination of the expression of the ABCB1/MDR1 and AMPK gene with the methodology described above. At the end of remission induction, metformin will be discontinued in group assigned to it.

Patients will be followed up for 12 months from the start of treatment, and any relapses of the disease or deaths, as well as the time at which they were diagnosed, will be recorded on the data collection sheet.

STATISTICAL ANALYSIS

Data analysis will be carried out using the Statistical Package for Social Sciences (SPSS) version 25.0. Descriptive data will be expressed in percentages and absolute values for qualitative variables, and will be described in medians, ranges, means and standard deviation for quantitative variables.

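### A single fixed block size of 6, stated in the protocol of a one-hospital trial with no masking or concealment described, would let a recruiter who keeps a tally foresee about 4.5 of the 20 assignments

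*Combined protocol and SAP*

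**What the plan says.** Under PROCEDURES, "patients will be randomized into 2 groups". The method is block randomisation with a random-digit table, described like this: "two-digit numbers are selected, each of which corresponds to a block of 6 patients, to which the intervention is assigned in the corresponding sequence". No other block size is mentioned, and nothing says that the size varies.

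The Sample size section sets the target: "10 patients are calculated for each group", so 20 in total. The allocation ratio within a block is not written down.

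The Population section and the inclusion criteria place all recruitment at one hospital, from February 2021 to December 2023. PROCEDURES states that newly diagnosed patients there "will be invited to participate in this trial, and informed consent will be requested from parents and participants". Both groups receive conventional induction, and the intervention group also receives oral metformin. No placebo or other masking is described.

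No section says who generates the list, who holds it, how it is concealed, or at what step an assignment is released. The ethics section does offer random assignment by blocks as the safeguard of fairness.

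**The concern.** Block randomisation with one known size becomes predictable towards the end of each block. Once one arm has used its places, every remaining assignment in that block is fixed. Three features of this plan make that usable: the size is in the protocol, one hospital's team can see every past assignment, and the treatment is not masked.

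Recruitment is slow. The window is 35 months, so 20 patients arrive on average 35/20 = 1.75 months apart, and keeping count takes no effort. Leukocyte count and immunophenotype come from the chart at diagnosis, so prognostic information may be at hand when a patient is invited.

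The risk is selection bias. If someone who foresees the next arm invites, or does not invite, a particular adolescent for that reason, the arms stop being comparable. With 10 per arm, one steered patient is 10% of an arm and two are 20%. The STATISTICAL ANALYSIS section plans between-group t, Mann-Whitney, chi-square or Fisher tests and log-rank tests, none of them adjusted for baseline factors. An imbalance created in this way would pass straight into the expression, response and survival comparisons.

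**Working it through.** **Inputs.** Block size 6 and two arms (PROCEDURES). Planned total 2 × 10 = 20 (Sample size; the loss step reproduces, since 8/(1 − 0.20) = 10, and how the 8 was reached does not affect this point). A 3:3 split within blocks is assumed from the equal group sizes. The plan gives no predictability figure of its own to reproduce.

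**Assignments certain in advance.** There are C(6,3) = 20 equally likely 3:3 arrangements. An assignment is certain when one arm has already used its three places.

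- Positions 1 to 3: never certain, probability 0.
- Position 4: the first three are all the same arm, 2/20 = 0.10.
- Position 5: one arm has three of the first four, 2 × C(4,3)/20 = 8/20 = 0.40.
- Position 6: always certain, 1.00.

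The sum is 0.10 + 0.40 + 1.00 = 1.5 per full block, and 1.5/6 = 25%. Every full block has at least one certain assignment: exactly one in 60% of blocks, two in 30% and three in 10%.

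Twenty patients make three full blocks plus two patients. The first two places are never certain, so the total is 3 × 1.5 = 4.5, and 4.5/20 = 22.5%.

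**Best guess.** The recruiter guesses the arm that is behind and tosses a coin when the arms are level. The chance of being right, by position, is:

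- 1: 0.5
- 2: 3/5 = 0.6
- 3: 0.4 × 3/4 + 0.6 × 1/2 = 0.6
- 4: 0.1 × 1 + 0.9 × 2/3 = 0.7
- 5: 0.4 × 1 + 0.6 × 1/2 = 0.7
- 6: 1

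The sum is 4.1 per block (68.3%). Over 20 patients it is 3 × 4.1 + 0.5 + 0.6 = 13.4, or 67%, against 10 by chance.

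**Sensitivity to the assumed split.** With 2:4 blocks, 1.73 of 6 (28.9%) would be certain, so the finding does not hang on 3:3.

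**Other known fixed sizes, 1:1.** Blocks of 4 give 33.3% certain and blocks of 8 give 20.0%. Choosing a different fixed, published size does not solve the problem.

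**Incomplete fourth block.** The first two places of a block of 6 are split 1:1 with probability 3/5 = 0.60. At 20 patients the arms are therefore 10:10 with probability 0.60, and otherwise 11:9.

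**The case against.** The other side has a fair case. The figures need a recruiter who knows the block size, keeps a tally and has discretion over invitations, and the documents do not say who recruits or who sees the list. There are only two exclusion criteria, so eligibility leaves little judgement to exploit. The general objective rests on a laboratory measure.

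Part of this stands. The figures describe what a recruiter could know; a reader might infer that recruiters do know, or do steer, and nothing in the documents shows that. The rest does not remove the point. Simply not inviting a patient needs no eligibility judgement. A laboratory endpoint guards against biased measurement, not against biased entry into the arms.

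Three further inferences are tempting and are not supported:

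- **That 20 not being a multiple of 6 is a defect.** The worst split is 11:9, and the incomplete block adds no certain assignment.
- **That no analysis could recover the bias.** Age, leukocyte count, hemoglobin, platelets, immunophenotype and pre-treatment expression are all collected. Imbalance in these can be seen and, within the limits of 20 patients, adjusted for. Only unmeasured factors escape. The fair criticism is that no adjustment is planned.
- **That one random permutation of 10 and 10 must replace the blocks.** It lowers certain assignments from 4.5 to 20/11 = 1.8, but correct guesses only from 13.4 to 12.3. At 10 patients the chance of a 7:3 split or worse is 33,052/184,756 = 18%, where blocks of 6 can do no worse than 6:4. It also leaves no assignment for a 21st patient. It is a trade-off, not a clear improvement.

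**Conclusion.** The point holds as a weakness in the stated method, and it is more than a missing detail: followed as written, the fixed-block rule leaves at least one foreseeable assignment in every full block. The size is 1.5 of 6 per full block (25%), about 4.5 of the planned 20 (22.5%), and about 67% correct guesses against 50%.

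This rests on a 3:3 split within blocks, a recruiter who knows the size and counts, and the absence of any concealment beyond what is described. The arithmetic is exact under those assumptions. Whether any steering would occur, and how far it would move the results, cannot be judged from the documents. The change is advisable because it is cheap and the trial is too small to absorb one or two steered patients.

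**What to change.** Change the assignment paragraph in PROCEDURES as follows:

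1. Remove the block size from the investigators' protocol and keep it in a separate document with restricted access.
2. Use randomly varied block sizes in place of a fixed 6.
3. Have the list generated by computer and held by a named role already in post that does not recruit.
4. Release each assignment only after consent, eligibility and the baseline sample are logged.

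As long as the sizes stay undisclosed, a recruiter can no longer tell when an assignment is certain. Guessing the arm that is behind still beats chance in an unmasked trial, because that guess needs only a tally and not the block size. Steps 3 and 4 matter for that reason: they keep the list itself away from recruiters, and they fix the patient's entry before the arm is revealed.

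The cost is one paragraph of text, a new list and slightly more list administration. The split at 20 patients may differ a little from 10:10. No extra patients are needed.

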The Kolmogorov-Smirnov test will be performed for continuous variables to determine if they have normal distribution; if they have normal distribution, both groups will be analyzed by means of the t-student test; if they do not have normal distribution, the chi-square test, Fisher's exact test and Mann Whitney U test will be used for the bivariate analysis. To compare the expression of ABCB1/MDR1 and AMPK genes at the time of diagnosis and at the end of induction, McNemar's test will be used.

For the calculation of the overall and disease-free survival function, the Kaplan Meier survival test will be used for both groups and the differences between groups will be analyzed by means of the log Rank test, both for overall and disease-free survival. Similarly, the overall and disease-free survival function will be analyzed with the Kaplan Meier test and log rank for ABCB1/MDR1 and AMPK gene expression.

ETHICAL AND BIOSAFETY ASPECTS

According to the General Health Law regarding research on human subjects, this protocol is considered a higher than minimal risk research, since randomized methods of assignment to therapeutic schemes are used.

This protocol takes into account the Mexican General Health Law regarding the provision of health care services and health research, as well as national and international ethical standards.

This study will be carried out with strict observance of recognized scientific principles and respect and confidential handling of the data obtained. The security mechanisms to maintain the ethical aspects of this study are:

1. Review of this protocol by the research and ethics committees of the Hospital General de México "[name]".
2. All information obtained in this study will be made available to the Ethics and Research Committees.
3. The confidentiality of the study information is assured, as well as the identity of the patients. The identification data of the participants will be codified, assigning a consecutive participation number. The identification information and the relation between the identification numbers and the data obtained will be known only to the participating investigators and will be preserved confidentially in electronic media.
4. There will be no charge for the study, nor will there be any consistency for participation in this study. Refusal to participate in the study will not influence the patient's treatment or clinical care.

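### The only test assigned to the change in gene expression compares time points, not arms, so it cannot show a metformin effect

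*Combined protocol and SAP*

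**What the plan says.** - **Question.** The Hypothesis is that metformin added to standard chemotherapy lowers ABCB1/MDR1 expression and raises AMPK expression by the end of induction. The second specific objective compares expression at diagnosis and at the end of induction between patients on conventional chemotherapy and patients who also receive metformin.
- **Treatment.** Procedures randomises to two groups, "where in both cases the conventional remission induction treatment will be given"; the intervention group also receives metformin.
- **Test for expression.** Statistical Analysis names McNemar's test for this purpose: "To compare the expression of ABCB1/MDR1 and AMPK genes at the time of diagnosis and at the end of induction". It does not say whether the test is run in each arm or in all patients together.
- **Other tests.** The t-test is listed for comparing both groups when continuous variables are normally distributed. Otherwise chi-square, Fisher's "exact test and Mann Whitney U test will be used for the bivariate analysis". None of these is linked to expression or its change. The log-rank test is linked to expression only as a factor for survival.
- **Scale.** The variable table codes expression as not expressed, high or low. Procedures measures mRNA levels by TaqMan and sets the cut-off this way: "The cut-off point between low and high expression will be determined according to mean values obtained in healthy controls".
- **Specimen.** Procedures first says "Peripheral blood samples will be collected in EDTA tube" and, of the expression assay, "This will be done on samples obtained before the start of treatment and at the end of the induction phase". Later, the sentence that opens "A bone marrow aspirate will be performed at the end of remission induction to evaluate the response to this phase of treatment" goes on to add "as well as determination of the expression of the ABCB1/MDR1 and AMPK gene with the methodology described above".

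**The concern.** A paired test in treated patients answers whether expression differed between two dates. Between those dates every patient receives a steroid pre-phase and multi-drug induction. The documents do not say what that treatment alone does to measured expression; the Problem Statement says that how these genes vary during treatment is unknown. A significant McNemar result in the metformin arm, or in all patients pooled, therefore fits a metformin effect, a chemotherapy effect, or both.

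The control arm exists to separate these. If an analyst follows the one sentence that names expression, the randomised comparison is not used for the main objective, and a change over time may be reported as efficacy. Running McNemar's test in each arm and contrasting the two p-values does not repair this, because significant in one arm and not significant in the other is not a test of the difference.

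**Working it through.** **Inputs from the documents.** Sample size section: 8 per group, 10 per group after a 20% loss, and a 50% high-to-low switch after metformin.

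**Inputs assumed.** The control-arm switch rate and the rate of reversals (low to high); the documents give neither. Switch rates are taken as shares of all pairs in an arm. Tests are exact, two-sided, at 5%.

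**The plan's own figure.** The stated formula with p = q = 0.5 and d = 0.05 gives 1.96² × 0.25 / 0.05² ≈ 384.2, so 385 and not 8. The loss step does reproduce: 8/0.8 = 10. The mismatch is a separate matter; 8 and 10 are used below only as the planned arm sizes.

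**Step 1: what McNemar's test sees.** It uses discordant pairs only. With a falls and b rises, p = 2 × P(Bin(a+b, 0.5) ≥ max(a, b)). With no rises, five falls give 2 × 0.5⁵ = 0.0625 and six give 2 × 0.5⁶ = 0.031, so six are needed. Suppose 6 of 10 patients in each arm fall and none rises. McNemar gives p = 0.031 in each arm and, with 12 of 12 pooled, 2 × 0.5¹² = 0.0005. The arms are identical, and Fisher's test between them gives p = 1.0.

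**Step 2: how often this happens with no metformin effect (both arms switch at 50%).**

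*No reversals, 10 pairs:* P(X ≥ 6) = (210 + 120 + 45 + 10 + 1)/1024 = 386/1024 = 0.377.

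*No reversals, 8 pairs:* P(X ≥ 6) = (28 + 8 + 1)/256 = 37/256 = 0.145.

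*10% reversals, 10 pairs* (fall 0.5, rise 0.1, unchanged 0.4). Significance in the direction of a fall needs a ≥ 6 with b = 0, or a ≥ 8 with b = 1:
- b = 0: 0.0840 + 0.0600 + 0.0281 + 0.0078 + 0.0010 = 0.1809
- b = 1: 90 × 0.5⁸ × 0.1 × 0.4 + 10 × 0.5⁹ × 0.1 = 0.0141 + 0.0020 = 0.0160
- total 0.197

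*10% reversals, 8 pairs:* only a ≥ 6 with b = 0 counts: 0.0700 + 0.0250 + 0.0039 = 0.099.

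| Chance that McNemar is significant in the metformin arm | 8 pairs | 10 pairs |
|---|---|---|
| 50% switch, no reversals | 14% | 38% |
| 50% switch, 10% reversals | 10% | 20% |
| 30% switch, no reversals | 1% | 5% |
| 70% switch, no reversals | 55% | 85% |

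Pooling both arms at a 50% switch with no reversals gives 89% with 16 pairs and 98% with 20. Run per arm with 10 pairs, the test is significant in the metformin arm only in 0.377 × 0.623 = 23% of trials, although the arms do not differ.

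**Step 3: the between-arm test in the same situation.** Full enumeration of Fisher's exact test on the switch rate, 50% in both arms, rejects in 2.1% of trials at 8 per arm and 1.3% at 10.

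**Step 4: power of the between-arm test.** Metformin switch 50% (Sample size section), control rate assumed:

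| Control switch | 8 per arm | 10 per arm |
|---|---|---|
| 0% | 36% | 62% |
| 10% | 22% | 30% |
| 20% | 12% | 13% |

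These figures let every patient count. If only patients with high expression at diagnosis can switch, the effective numbers are smaller and power is lower.

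**The case against.** The strongest reply is that the plan already has between-group tests. Statistical Analysis speaks of analysing both groups and lists four such tests, expression is a listed variable, and the second objective compares the arms. On that reading the general tests cover expression and McNemar's test adds the paired view. Much of this stands: a reader might infer that the plan has no between-arm test at all, and the documents do not support that. Nor do they state that the metformin conclusion will rest on McNemar's test. What remains is that no between-arm test is assigned to expression or its change, while the one sentence about expression over time points to a test that ignores arm.

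A second reply is that the rates in the illustration are assumed. That also stands. With a 30% switch the rejection rates are 1% and 5%, no higher than the nominal level, and reversals reduce the 50% figures. The argument does not depend on any of these rates, because McNemar's test does not use arm in any scenario.

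A reader might also infer that the plan pairs blood at diagnosis with marrow at the end of induction. The documents do not support that. Procedures names peripheral blood by vein puncture at both times, the aspirate sentence refers back to that method, and the induction schedule has separate rows for the aspirate and for expression. Following the plan gives blood at both times; the aspirate sentence is only loosely worded.

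**Conclusion.** The point holds as a gap in the analysis plan. McNemar's test is the only test assigned to the expression change. Whether run per arm or pooled, it cannot test the difference between arms that the hypothesis and second specific objective require, and induction chemotherapy in both arms means a before/after change cannot be attributed to metformin.

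With no metformin effect and an assumed 50% switch in both arms, the metformin arm shows a significant change in 38% of trials (10 pairs, no reversals) or 20% (10% reversals); with 8 pairs, 14% or 10%. A between-arm Fisher test rejects in 1% to 2%. The McNemar rates are not error rates of that test, since expression does change over time in these scenarios; they show how often the change could be misread as a drug effect. They rest on assumed rates and are not predictions for this trial.

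The specimen wording is a minor clarification and carries no weight in this conclusion.

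**What to change.** In Statistical Analysis:
1. State that McNemar's test is run within each arm and is descriptive.
2. Base the metformin conclusion on a randomised between-arm comparison that uses both time points. One option is Fisher's exact test on the proportion switching from high to low ABCB1/MDR1, and from low to high AMPK. Another is a Mann-Whitney test on the change in the TaqMan mRNA level. Both tests are already named in the plan. Choose one in advance.
3. Report the between-arm difference with its 95% confidence interval.
4. If the categorical version is chosen, state how the not-expressed category is grouped and which patients form the denominator.

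In Procedures, reword the aspirate sentence so that it agrees with the earlier text on the end-of-induction specimen.

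**Cost.** A few sentences and no added patient procedure, since both expression samples are already planned. The real price is power: at these arm sizes the between-arm Fisher test reaches at most 62% in the scenarios above and falls to 12% or 13% when 20% of controls also switch. The before/after p-value would no longer support an efficacy claim, so the interval becomes the main result to read.
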